5.2. Exclusion Criteria

- Pre-existing Familial adenomatous polyposis, inflammatory bowel disease or ulcerative colitis
- Active gastritis or active peptic ulcer
- History of continuous daily use of PPI more than 1 year prior to consent
- Gastrointestinal bleeding within the past one year
- Haemorrhagic diathesis (i.e. haemophilia)
- Uncontrolled hypertension (untreated systolic blood pressure > 160 mmHg, or diastolic blood pressure > 95 mmHg)
- History of recent cancers (except for colorectal cancers, non-melanoma skin cancers, basal cell carcinomas, squamous cell carcinomas) in the past 5 years
- History of stroke, coronary arterial disease, angina, or vascular disease
- Patients who are on current long term treatment (\geq 4 consecutive weeks) with Aspirin, NSAID or Cox-2 inhibitors
- History of erosive GERD or active erosive GERD on gastroscopy.
- Patient on active current treatment of antiplatelet agents (i.e. off-study Aspirin, clopidogrel, ticlopidine)
- Patient receiving active treatment of anticoagulants (i.e. warfarin, low molecular weight heparins)
- Pregnant, lactating, or not using adequate contraception
- Patient having known allergy to NSAID or Aspirin
- Unexplained rise of CEA (i.e. smoker with elevated CEA will not be excluded)
- Patient on other investigational drug
- Patients with HNPCC (Lynch Syndrome)

6. RANDOMISATION

Randomization will occur within 120 days of completion of standard therapy. After informed consent is signed and subject's eligibility is confirmed, the subject can be randomised in a 1:1 allocation ratio, stratified by

- Study centre
- Tumour type (Dukes C colon, high risk Dukes B colon cancer, and rectal cancer sub-groups) and
- Type of adjuvant chemotherapy received (exposed/ not exposed to oxaliplatin)

to receive either Aspirin or a matched placebo for 3 years.

Randomisation will be done via direct web randomisation: Authorized study centre personnel will randomise the patient via a password-protected internet web site. The randomisation system will then determine the treatment arm and provide the subject number to be used for the patient. The site monitor/ project coordinator will be informed immediately in the event that the web randomisation is not successful.

7. STUDY DRUG

7.1. How to take the study drug

The study subject will take two tablets of study drug orally daily for 3 years or as instructed by investigator.

7.2. Supply and Resupply of study drug

The investigator or designated person at the study centre will dispense the study drug to the patient at baseline visit and each assessment/ follow-up visit. Patients are required to return the used and unused bottles at each visit for drug accountability.

Each subject will be given sufficient supply at each follow-up visit to the study centre according to the specified protocol schedule during the first 3 years after randomisation. If the subject requires treatment modification (dose reduction), study drug supply will be adjusted and dispensed as appropriate.

The manufacturer of study drug, Bayer AG, will provide the required study drugs for this study. These are being shipped from Bayer AG to the central drug depot. The central drug depot will then be responsible for the distribution to the individual study centres. The study centre PI is responsible to ensure that there are adequate supplies for the study subjects at the centre.

7.3. Description and contents of study drug and placebo drug

Each tablet contains 100 mg enteric-coated Aspirin (Acetylsalicylic acid) or placebo. Excipients of Aspirin Cardio placebo include: microcrystalline cellulose, citric acid anhydrous, dibasic hydrogen phosphate, lactose monohydrate, magnesium stearate of vegetable origin, maize starch, silica colloidal anhydrous, methacrylic acid-ethyl acrylate copolymer, talc, triethylcitrate.

7.4. Packaging information

Each tablet contains 100 mg enteric-coated Aspirin (Acetylsalicylic acid) or placebo. Study drug will be supplied in screw capped bottles with 100 tablets per bottle and two bottles of study drug will be packed in a secondary packaging box. This would be sufficient for 100 days for one subject.

7.5. Storage information

Study drugs at each centre must be stored in a secure and locked facility and in a dry place, at room temperature (25 degree centigrade and below). Any temperature deviation must be reported once known, to the site monitor or project coordinator who will in turn report to the project manager of the trial at NCCS.

Following exposure to a temperature deviation, study drugs will not be used until approval is given by the manufacturer through the trial project manager via the site monitor or project coordinator.

7.6. Study drug labelling and handling

The primary label of the study drugs will be labelled through Bayer AG centrally and delivered to the allocated depots. The kit numbers will be labelled by unblinded personnel at the allocated depots before delivering to the individual study centres in batches.

The label will include the following particulars (Appendix IV – Study Drug Label):

- a) the study protocol code
- b) batch number
- c) Manufacture date, expiry date or retest date of study material
- d) the subject number for whom the study material is intended
- e) The study site code
- f) Dosage and administration instruction
- g) the storage conditions, as indicated by the manufacturer
- h) the words : “ For clinical trial use only”
- i) the name and address of the manufacturer

The study drug at site should be handled only by authorised personnel at site. The study drug accountability will also be done by authorised personnel and all the procedures will be documented. The authorised personnel at site is also responsible of the destruction of the unused or returned study drug as per institution practice after the study drug accountability is documented checked.

The investigator at each study centre should ensure that the investigational product(s) are used only in accordance with the approved protocol.

7.7. Compliance of study drug

Noncompliance is defined as omission of more than 30% of days for the study period during which the patient is on the study drug. The reason for non-compliance will be documented.

7.8. Anticipated side effects of Aspirin

Side effects that occasionally occur are gastrointestinal disorders such as nausea, vomiting, diarrhoea, and slight gastrointestinal blood loss which in exceptional cases can lead to anaemia. Gastrointestinal ulcers may rarely develop, in some circumstances with haemorrhaging and

perforation. Dizziness and ringing in the ear can occur as symptoms of over dosage, especially in children and elderly patients.

Rare cases of hypersensitivity reactions (e.g. difficulty in breathing, skin reaction) can occur.

Isolated cases of liver and kidney function disturbances, and severe skin reactions have been reported.

The absolute annual increase risk attributable to Aspirin for major bleeding, major gastrointestinal bleeding and intracranial haemorrhage is estimated at 0.13%, 0.12% and 0.03% respectively. (McQuaid KR et al)

8. BLINDING

8.1. Blinding

This is a double-blind study. The patient, the study team including the investigator(s) and the sponsor will be blinded. However, study statistician who prepares the randomisation list and the designated unblinded personnel who are involved in the procedures of study drug packaging and labelling will not be blinded.

8.2. Code-break envelopes

The study statistician will prepare the sealed emergency code-break envelopes and distribute to the study centres accordingly. The envelopes will contain the treatment assignment, with the corresponding subject number printed on it. The sealed emergency code-break envelopes will be collected before site closure or when necessary to return to the study statistician for destruction.

8.3. Unblinding

The emergency code-break envelopes provided by the study statistician will be kept at site by investigator or designated person. In case of medical emergency, unblinding should be done to the required subject only, where the study code needs to be known prior to the further management of subject. At such, the study centre investigator or designated person will unblind the treatment given to the subject. The investigator will discuss the purpose of unblinding with the study co-chair, if possible, prior to unblind the study patient. The study statistician and monitor/project coordinator will be informed of the occurrence and reason for unblinding. In the event of unblinding, only the investigator treating the patient will be unblinded of the treatment code & it is his primary responsibility to keep the rest of the study team at his centre blinded of the treatment code.

9. TREATMENT SCHEDULE

9.1. Treatment groups

The study drug, oral Aspirin 200 mg/ placebo 200 mg OD should be started immediately but no later than 2 weeks after randomisation/baseline visit. The patient will be treated with the same study drug for 3 years.

9.2. Treatment modification

The treatment modifications listed in this section are for reference only. The investigator should modify the treatment according to clinical judgement and best medical practices.

Event	Severity	Action
Angioedema	Any	Stop study drug permanently
Anaphylaxis	Any	Stop study drug permanently
Generalized Rashes	Any	- Stop study drug for two weeks - Consider to rechallenge at next follow up/ assessment if the rash is mild, or unlikely to be related to study drug
Epigastric discomfort	Mild	- Reduce dose to 100 mg of study drug - Start PPI - Review in one month. If symptoms persist, consider stopping study drug and gastroscopy (Treat as per Gastroscopic findings)
Epigastric discomfort	Moderate	- Stop study drug - Start PPI - Review in one month - Rechallenge with lower dose (i.e. 100 mg) of study drug if symptoms resolved and continue long term PPI therapy. - Consider gastroscopy if symptoms persist
Epigastric discomfort	Severe	- Stop study drug - Start PPI - Gastroscopy - Treat as per Gastroscopic findings
Haematemesis	-	- Stop study drug permanently - Start PPI - Gastroscopy - Treat as per Gastroscopic findings
Melenic stools	-	- Stop study drug permanently - Start PPI - Gastroscopy with/without colonoscopy - Treat as per Gastroscopic findings
Asymptomatic drop in haemoglobin of > 2 g/dL from baseline	-	- Stop study drug - Start PPI - Gastroscopy/Colonoscopy - Treat as per Gastroscopic findings

Gastroscopic Findings

Event	Severity	Action
Gastritis	Mild/ Moderate	- Stop study drug - Start PPI - Rechallenge with lower dose (i.e. 100 mg) of study drug 2- 4 weeks after therapy with PPI - Helicobacter pylori eradication if present
Gastritis	Severe	- Stop study drug (for 4-8 weeks) - Start with PPI

		
 - Consider rechallenge with lower dose (i.e. 100 mg) of study drug 4-8 weeks after therapy with PPI if symptoms resolved completely - Helicobacter pylori eradication if present
Peptic ulcer	-	
 - Stop study drug permanently - Start PPI - Helicobacter pylori eradication if present
Oesophageal or Gastric Varices	-	
 - Stop study drug permanently - Continue on follow up as per institutional practice - Helicobacter pylori eradication if present
Normal findings in a symptomatic patient	-	
 - Consider other cause of symptoms - Continue study drug at lower dose (i.e. 100 mg) together with PPI - Consider to stop study drug if symptoms are severe and persistent despite treatment with PPI

Patients who are unable to tolerate 200 mg of study drug may have the dose reduced to 100 mg of study drug. The reason and date of dose reduction will be clearly documented. PPIs will be used in patients who have symptoms of epigastric discomfort. They should be given at adequate doses and continued for at least 3 months. PPIs are preferable to H2 antagonists. Antacids (i.e. magnesium trisilicate, magnesium carbonate) should not be given in place of PPIs; however, they may be used to supplement these agents. Patients who undergo gastroscopy should be screened for helicobacter pylori. Positive helicobacter pylori should be treated accordingly.

Patients who develop anaphylaxis, angioedema or gastrointestinal bleeding should stop the study drug immediately and should not undergo rechallenge to study drug.

Patients who need to undergo elective surgery or other interventional procedures may stop the study drug 5 days prior to surgery and recommence the study drug upon recovery (when haemostasis is secured or when the patient is able to take orally).

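### Protocol 9.2 stops study drug permanently after haematemesis or melaena, then refers the patient without exception to a gastroscopy table whose gastritis rows direct or allow rechallenge at 100 mg

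*Protocol*

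**What the plan says.** All the text at issue is in Protocol 9.2 (Treatment modification), which has an event table, a Gastroscopic Findings table and closing paragraphs.

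- **Status of the section.** It opens with "The treatment modifications listed in this section are for reference only" and leaves modification to clinical judgement.
- **Haematemesis row.** "Stop study drug permanently - Start PPI - Gastroscopy - Treat as per Gastroscopic findings"
- **Melenic stools row.** "Stop study drug permanently - Start PPI - Gastroscopy with/without colonoscopy - Treat as per Gastroscopic findings"
- **Findings table, mild or moderate gastritis.** After stopping the drug and starting a PPI: "Rechallenge with lower dose (i.e. 100 mg) of study drug 2- 4 weeks after therapy with PPI"
- **Findings table, severe gastritis.** "Consider rechallenge with lower dose (i.e. 100 mg) of study drug 4-8 weeks after therapy with PPI if symptoms resolved completely"
- **Findings table, normal findings in a symptomatic patient.** "Continue study drug at lower dose (i.e. 100 mg) together with PPI"
- **Findings table, peptic ulcer and varices.** Both rows stop study drug permanently.
- **Closing text.** "Patients who develop anaphylaxis, angioedema or gastrointestinal bleeding should stop the study drug immediately and should not undergo rechallenge to study drug"
- **Haemoglobin row of the event table.** For "Asymptomatic drop in haemoglobin of > 2 g/dL from baseline" the action is to stop study drug (the word permanently is absent), start a PPI, perform endoscopy and follow the same referral.

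**The concern.** A patient with haematemesis or melaena meets a permanent stop and, in the same table cell, a referral to a second table that sets its own study-drug actions. Some of those actions lead back to study drug. An investigator who follows the referral literally could re-expose a patient who has bled, which the closing text of the same section rules out.

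The matter concerns participant safety first. Protocol 7.8 and 13.1 name gastrointestinal effects, including bleeding, among the expected harms of aspirin. It also touches what is recorded: SAP 4.4 summarises discontinuation and exposure by group, and SAP Table 10 classes the action taken after a serious event as modified to 100 mg, interrupted or permanently discontinued. Those entries should reflect one protocol rule.

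**Working it through.** There is no figure to recompute; the check sets the rows against each other.

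**Step 1. Entry rows for overt bleeding.** There are two, haematemesis and melaena. Each says permanent stop and each ends with the referral to the gastroscopic findings. Neither limits what the referral covers.

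**Step 2. Where the referral leads.** No row of the findings table mentions how the patient arrived there.

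| Gastroscopic finding | Study-drug action in the table | Against a permanent stop |
|---|---|---|
| Gastritis, mild or moderate | Rechallenge at 100 mg | Contradicts |
| Gastritis, severe | Consider rechallenge at 100 mg if symptoms have resolved | Reopens the question |
| Normal, symptomatic patient | Continue at 100 mg | Contradicts only if the bleed is read as a symptom |
| Peptic ulcer | Permanent stop | Agrees |
| Varices | Permanent stop | Agrees |

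Two entry rows by five findings give 10 combinations: 2 × 2 = 4 agree, 2 × 1 = 2 contradict outright, 2 × 1 = 2 reopen the question, and 2 × 1 = 2 depend on the reading (4 + 2 + 2 + 2 = 10).

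**Step 3. The closing sentence.** It names gastrointestinal bleeding and excludes rechallenge, so it sides with both entry rows. It does not say that it takes precedence over the findings table.

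**Step 4. The opening sentence.** It covers the modifications listed in the section. It does not say whether the closing prohibition is also only for reference.

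**Step 5. The haemoglobin drop.** This row has no permanent stop, so a later rechallenge row does not contradict it. If gastritis is found, the gastritis rows direct or allow rechallenge. The closing sentence forbids it only if the drop counts as gastrointestinal bleeding, and 9.2 does not define that term. Other sections do not settle it: Protocol 7.8 describes slight blood loss that can lead to anaemia, whereas 11.7 records major bleeding that needs transfusion. Separately, an asymptomatic drop with normal endoscopy has no row, because the only normal-findings row is for a symptomatic patient. That is an omission, not a contradiction.

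**The case against.** The strongest reply is that 9.2, read as a whole, already gives the answer for overt bleeding. Both entry rows and the closing sentence point the same way, and only a general cross-reference pulls against them. The findings table also has a proper use without conflict: severe epigastric discomfort, persisting mild epigastric discomfort and the haemoglobin drop all reach it without a permanent stop. For the bleeding rows, the referral could mean treating the lesion (PPI, *Helicobacter pylori* eradication) and no more. The normal-findings row fits a bleed poorly, since one cannot continue a drug already stopped for good, and its wording suits epigastric symptoms better.

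Much of this stands. The two sides are not of equal weight, and the normal-findings case is the weakest of the three. The lesion-only reading is possible but nothing signals it. The same referral ends the severe epigastric discomfort and haemoglobin rows, which give a plain stop and no restart rule, so there the findings table supplies the study-drug decision. A reader is not told that the same words mean less in the bleeding rows. The reference-only label does not settle the conflict either, because it may weaken the prohibition as much as the tables.

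Two stronger readings are tempting, and the documents do not support them.

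- **That all three bleeding-related entry rows conflict with a permanent stop.** The haemoglobin row contains no permanent stop.
- **That sites will act differently and so distort discontinuation, exposure or repeat-bleed counts between arms.** The documents contain nothing on how sites act. The one scale they offer is the 0.12% annual excess of major gastrointestinal bleeding in Protocol 7.8. With 1587 / 2 = 793.5 patients per arm and 3 years of full exposure at a constant excess, that is 793.5 × 0.0012 × 3 ≈ 2.9 extra patients. Minor bleeds and haemoglobin drops are not counted, so this is not an upper bound, but it is no evidence of a material between-arm effect. Patients who stop treatment are followed to 5 years (Protocol 9.3 and 9.4), and efficacy is analysed as randomised among those who started treatment (SAP 4.2), so stopping or restarting removes nobody from the primary comparison.

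**Conclusion.** The inconsistency is real and stands in the current text, but it is narrow. For overt bleeding, the referral in two entry rows leads to one finding that contradicts the permanent stop, one that reopens it, and one that contradicts it only on a particular reading. The other two findings agree with it. The closing sentence supports the permanent stop without being given precedence. The haemoglobin drop is a secondary ambiguity that turns on an undefined term.

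The conclusion rests on reading the referral literally, as including the study-drug actions in the table it points to. It does not rest on any view of which clinical rule is right. Sample size, power and type I error are untouched. The point merits correction because it concerns conflicting instructions on re-exposure after an expected harm of the drug, and because the correction is cheap.

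**What to change.** Reconcile the passages of 9.2 so that each combination of entry event and gastroscopic finding yields one study-drug action:

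1. State in the Gastroscopic Findings table which entry events its study-drug actions apply to.
2. State whether a haemoglobin drop with an endoscopic source falls under the closing sentence on gastrointestinal bleeding, and what applies when an asymptomatic drop has normal endoscopy.
3. State whether the closing sentence is binding although the section describes its modifications as reference only.

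The content of each rule is for the sponsor's clinicians. The cost is a wording amendment to one section and its two tables, with a memo to sites. No procedure, visit or analysis is added.

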9.3. Treatment discontinuation

The investigator has the right to discontinue study treatment if he/she feels that it is in the best interests of the patient or due to safety concerns.

Study drug will be stopped immediately if there is disease recurrence confirmed by CT, histology or cytology, and in the event of an SAE unequivocally related to study drug (or at the discretion of the investigator if the relationship of SAE to the study drug cannot be established with certainty at the time of reporting).

The reasons for treatment discontinuation will be documented. Patients with their treatment discontinued will continue to be followed up until 5 years after randomisation.

Even if a patient chooses not to adhere to the treatment assignment or data collection schedule, every effort should be made to follow patient for the protocol objectives until the end of the study.

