3. STUDY ENDPOINTS

Primary endpoints

- DFS among all eligible subjects (high risk Dukes B colon cancer, Dukes C colon cancer and rectal cancer patient sub-groups);
- DFS among patients with colon cancer (high-risk Dukes B and Dukes C colon cancer).

Secondary endpoints

- Overall survival (OS) over 5 years
- DFS and OS in
 - Chinese, Malay, Indian and other ethnic groups
 - Resected high risk Dukes B colon cancer, Dukes C colon cancer and rectal cancer sub-groups, individually
 - Compliant versus non-compliant subjects
 - PIK3CA mutated tumors (where samples are available)

Endpoint definitions

Disease recurrence is defined as any one of the followings:

1. Unequivocal radiological evidence of colorectal cancer recurrence
2. Recurrence detected by Digital rectal examination (DRE)
3. Positive histology or cytology (i.e. peritoneal or pleural cytology)
4. Colonoscopic evidence of local cancer recurrence at the previous operation site
5. Detection of a new colon or rectal primary tumour

Disease free survival is defined as the time from randomisation to the time of documentation of disease recurrence or death from any cause. If there is no disease recurrence or death by the time when a patient is last followed up, it will be censored at that time.

Overall survival is defined as the time from randomisation to the time of death from any cause. If there is no death by the time when a patient is last known to be alive, it will be censored at that time.

Compliant subject is defined as a subject who takes the study drug for more than 70% of days for the study period during which the patient is on treatment, up to the time of discontinuation.

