- Subjects with recurrence (who may be receiving salvage treatment or palliative care) may be assessed at 6 monthly intervals in the clinic or via phone assessments if they are unable to return for 3 monthly clinic follow up. Hb, CEA, and concomitant medication data are not required after recurrence date.

11.4. 6-monthly assessments

6-monthly assessments will be done at month 42, 48, 54 and 60.

Assessments \pm 1 month window will be allowed for each 6-monthly visit. The following will be performed at each assessment:

- CEA
- Death and related information if any
- Medical Events: (AMI, transient ischemic attack, stroke, new cancers and gastrointestinal bleeding)
- Concomitant NSAIDs
- Recurrence and salvage chemotherapy
- Subjects with recurrence (who may be receiving salvage treatment or palliative care) may be assessed via phone assessments if they are unable to return for clinic follow up. CEA is not required after recurrence date.

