11.6. Assessment of recurrence and salvage chemotherapy

For the patient with unequivocal radiological documented recurrence, the date of CT scan or any other radiological modality documenting unequivocal recurrence will be taken as the date of recurrence. Patients who have disease recurrence confirmed with histology or cytology, the date of recurrence will be taken as the date of biopsy or cytology collection.

For patients with local recurrence detected through colonoscopy/CT colonogram or digital rectal examination (DRE), without CT scan or histology, the date of colonoscopy or DRE will be taken as the date of recurrence.

An elevated CEA level or abnormal LFT will not be considered as acceptable evidence of colorectal cancer recurrence. However, a rising CEA trend should prompt the search for possible tumour recurrence.

At the time of colorectal cancer recurrence, the investigator should clearly indicate the site of tumour recurrence and the method of diagnosis.

Patients with tumour recurrence and commencing salvage chemotherapy will have the names and initiation date of each new chemotherapy regimen recorded.

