3.2 Treatment Schedule

A total of 1587 subjects will be randomised from multinational centres. After randomisation, subject will have 3-monthly assessments for 3 years (month 3 to month 36) followed by 6-monthly assessments for additional 2 years (month 42 to month 60). Subjects who consent to continue information collection after month 60 will have vital data captured via review of medical records or phone call.

The study drug, oral Aspirin 200 mg/ placebo 200 mg once a day, should begin immediately but no later than 2 weeks of randomisation. The study drug will be stopped immediately if there is a disease recurrence confirmed by CT, histology or cytology. In the event of SAE related to the study drug, the study drug will be stopped immediately.

The investigator has the right to discontinue study treatment if he/she feels that it is in the best interests of the subject or due to safety concerns. The reasons for treatment discontinuation will be documented. All subjects, including subjects who discontinued from study treatment, will continue to be followed for 5 years after randomisation, unless the subject is lost to follow up, died or withdrew consent.

3.3

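### Study drug must stop on fewer kinds of recurrence than the DFS endpoint counts, and scheduled haemoglobin ends at the recurrence date even if the drug continues

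*Protocol*

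**What the plan says.** **Stop rule.** Protocol 9.3: "Study drug will be stopped immediately if there is disease recurrence confirmed by CT, histology or cytology". SAP 3.2: "The study drug will be stopped immediately if there is a disease recurrence confirmed by CT, histology or cytology". Protocol 9.3 also lets the investigator stop treatment at discretion.

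**Endpoint.** Protocol section 3: "Disease free survival is defined as the time from randomisation to the time of documentation of disease recurrence or death from any cause". Its routes to recurrence include "Unequivocal radiological evidence of colorectal cancer recurrence", DRE, colonoscopic local recurrence, histology or cytology, and a new colorectal primary. SAP section 3 repeats the list. Protocol 11.6 dates a radiological recurrence by CT or any other modality. For local recurrence found at colonoscopy or DRE it adds: "without CT scan or histology, the date of colonoscopy or DRE will be taken as the date of recurrence".

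**Data collection.** Protocol 11.3: "Hb, CEA, and concomitant medication data are not required after recurrence date". SAP 3.4 says the same. In the protocol's visit schedule (Summary and Appendix 3), the After Recurrence column has no mark for Hb, AE/SAE or concomitant medication.

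**Text pointing the other way.** Protocol section 10 records concomitant medication until 30 days after treatment discontinuation. Protocol 13.2 records AEs and SAEs until 30 days after study drug ends.

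**Rule that uses Hb.** The treatment-modification table in Protocol 9.2 has an entry for "Asymptomatic drop in haemoglobin of > 2 g/dL from baseline".

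**The concern.** Two clocks should agree and do not. The endpoint clock starts at any counted recurrence. The drug-stop clock starts only at recurrence shown by CT, histology or cytology. The on-drug assessments are released by the endpoint clock, which makes sense only if the drug has already stopped.

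The mismatch is foreseeable in this trial. Dukes B and C rectal cancers are eligible, the imaging row of the schedule lists MRI, PET and ultrasound beside CT, and each centre sets its own surveillance policy. Whether a stop is mandatory can therefore depend on which test found the recurrence and where.

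At stake is a small safety gap: a patient who may still be taking aspirin no longer has a scheduled check for occult blood loss. Sites also face conflicting instructions on how long to record concomitant medication and adverse events.

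**Working it through.** The plan states no figure on this point. The check compares the texts.

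**Step 1. Which findings count, and which force a stop?**

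| Finding | Counted DFS event (Protocol 3, 11.6; SAP 3) | Mandatory stop (Protocol 9.3; SAP 3.2) |
|---|---|---|
| CT | Yes | Yes |
| Histology or cytology | Yes | Yes |
| Unequivocal MRI or ultrasound | Yes | No |
| PET | Yes | Not as worded; arguable if PET-CT is read as CT |
| DRE alone | Yes | No |
| Colonoscopy without biopsy | Yes | No |
| New colorectal primary | Yes | Only if also shown by CT, histology or cytology |

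Protocol 11.6 expressly provides for events with neither CT nor histology, so the gap does not depend on a strained reading.

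**Step 2. What ends each collection after a counted recurrence if the drug continues?**

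| Item | Text tied to recurrence | Text tied to drug stop |
|---|---|---|
| Hb | Not required (Protocol 11.3, SAP 3.4); no mark in the schedule | None for patients with recurrence |
| Concomitant medication | Not required (Protocol 11.3, SAP 3.4); no mark | Continues to 30 days after discontinuation (Protocol 10) |
| AE/SAE | No mark | Continues to 30 days after drug ends (Protocol 13.2) |
| NSAIDs, medical events, death | Still marked | Not affected |

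Hb is the only item with no text keeping it alive. For the other two the documents contradict themselves. For patients who discontinue early without recurrence, Protocol 11.3 does tie the end of Hb to the drug stop, so the right kind of anchor already exists one bullet away.

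**Step 3. What could one patient miss?** Suppose pelvic recurrence is unequivocal on MRI at month 10 and the drug is not stopped. Scheduled Hb falls at months 6, 12, 18, 24, 30 and 36, and treatment ends at month 36. The values no longer required are those at months 12, 18, 24, 30 and 36: (36 − 12)/6 + 1 = 5. That is the most for this illustration; any later stop of the drug, for whatever reason, lowers it.

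**The case against.** Much of the opposing case stands.

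- **Context of the waiver.** The Protocol 11.3 sentence sits under a sub-heading on early treatment discontinuation and describes patients who may be on salvage or palliative care. It was probably written for patients already off drug. But Protocol 9.3 does not ensure that they are, and neither SAP 3.4 nor the schedule column carries that limit.
- **Other routes off drug.** The investigator may stop at any time. Section 10 removes a patient from study treatment when anticancer treatment is required. A reader might infer that the drug runs until such treatment begins; the text says need, not start.
- **Deliberate design.** Protocol and SAP agree on the narrower stop rule, so it may be intended. That would explain the rule, but not why Hb is released while the drug may continue.

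Some stronger readings are tempting but not supported.

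- **That concomitant-medication and AE/SAE collection is switched off.** Section 10 and 13.2 keep both running, and unscheduled visits (11.5) also assess AEs and SAEs. This is a contradiction, not a clean stop.
- **That the Hb-drop rule cannot operate.** Not required is not forbidden, and the 9.2 table is offered as reference, subject to clinical judgement. What is lost is the scheduled value. Gastrointestinal bleeding is still captured as a medical event.
- **That efficacy results are distorted.** DFS is fixed at the event. OS is analysed as randomised (SAP 4.2). SAP compliance can end at recurrence, but SAP duration of exposure runs to the last dose, so continued exposure is still counted.

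**Conclusion.** The inconsistency is real in both documents. A counted DFS event need not trigger a drug stop, and scheduled Hb is released at the event date regardless. Alongside it are two contradictions: section 10 against 11.3 and SAP 3.4 on concomitant medication, and 13.2 against the visit schedule on AE/SAE.

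The number of patients cannot be derived, because the documents do not say how many recurrences are documented only by a route outside the stop rule. A reader might try a figure: if 5–15% of about 250 recurrences were of this kind, 0.05 × 250 = 12.5 and 0.15 × 250 = 37.5. Neither input is in the documents. The product also ignores recurrences after month 36, patients already off drug, and those stopped by discretion or by a need for anticancer treatment. It should not be read as an estimate. I assume that many such findings would soon go on to CT or biopsy, which would then trigger the stop. On that basis the number is probably small.

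The DFS definition, the target of 300 events and the sample size of 1587 are unaffected. This is a minor consistency and safety point.

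**What to change.** 1. **Reconcile the definitions.** The sponsor's clinicians should reconcile Protocol 9.3 and SAP 3.2 with Protocol sections 3 and 11.6 and SAP section 3. If the difference is intended, the documents should say so. Which stopping definition is right is for them to decide.

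2. **Tie release from on-drug assessments to the drug.** Reword Protocol 11.3, SAP 3.4 and the After Recurrence column in both copies of the schedule, so that release follows study-drug discontinuation and not the recurrence date. Use the anchors already in the protocol: drug stop for Hb (11.3, early-discontinuation bullet), and 30 days after drug stop for concomitant medication (section 10) and AE/SAE (13.2). The recurrence date should not enter this rule. A patient who stopped the drug long before recurring would otherwise be pulled back into assessments that those sections have already ended.

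3. **Count the cases (optional).** Compare last-dose and recurrence dates by method of diagnosis. SAP Table 7 already tabulates method, but pools all radiology. Separating CT from other modalities would need the detail on the recurrence form, if it is recorded there.

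The cost is wording in both documents, a few schedule marks, and a few extra six-monthly Hb values in patients still on drug after a counted recurrence. Patients then being followed by phone would need a blood test.
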